#### **10.1.5. Committees Structure**

##### **10.1.5.1. Data Monitoring Committee**

This study will not use an E-DMC.

#### 10.1.6. Dissemination of Clinical Study Data

Pfizer fulfills its commitment to publicly disclose clinical study results through posting the results of studies on [www.clinicaltrials.gov](http://www.clinicaltrials.gov) (ClinicalTrials.gov), the European Clinical Trials Database (EudraCT), and/or [www.pfizer.com](http://www.pfizer.com), and other public registries in accordance with applicable local laws/regulations. In addition, Pfizer reports study results outside of the requirements of local laws/regulations pursuant to its standard operating procedures (SOPs).

In all cases, study results are reported by Pfizer in an objective, accurate, balanced, and complete manner and are reported regardless of the outcome of the study or the country in which the study was conducted.

##### [www.clinicaltrials.gov](http://www.clinicaltrials.gov)

Pfizer posts clinical trial US Basic Results on [www.clinicaltrials.gov](http://www.clinicaltrials.gov) for Pfizer-sponsored interventional studies (conducted in patients) that evaluate the safety and/or efficacy of a product, regardless of the geographical location in which the study is conducted. US Basic Results are generally submitted for posting within 1 year of the primary completion date (PCD) for studies in adult populations or within 6 months of the PCD for studies in pediatric populations.

PCD is defined as the date that the final participant was examined or received an intervention for the purposes of final collection of data for the primary outcome, whether the clinical study concluded according to the prespecified protocol or was terminated.

##### EudraCT

Pfizer posts European Union (EU) Basic Results on EudraCT for all Pfizer sponsored interventional studies that are in scope of EU requirements. EU Basic Results are submitted for posting within 1 year of the PCD for studies in adult populations or within 6 months of the PCD for studies in pediatric populations.

##### [www.pfizer.com](http://www.pfizer.com)

Pfizer posts public disclosure synopses (CSR synopses in which any data that could be used to identify individual participants have been removed) on [www.pfizer.com](http://www.pfizer.com) for Pfizer sponsored interventional studies at the same time the US Basic Results document is posted to [www.clinicaltrials.gov](http://www.clinicaltrials.gov).

Documents within marketing authorization packages/submissions

Pfizer complies with the European Union Policy 0070, the proactive publication of clinical data to the European Medicines Agency (EMA) website. Clinical data, under Phase 1 of this policy, includes clinical overviews, clinical summaries, CSRs, and appendices containing the protocol and protocol amendments, sample CRFs, and statistical methods. Clinical data, under Phase 2 of this policy, includes the publishing of individual participant data. Policy 0070 applies to new marketing authorization applications submitted via the centralized procedure since 01 January 2015 and applications for line extensions and for new indications submitted via the centralized procedure since 01 July 2015.

Data Sharing

Pfizer provides researchers secure access to patient level data or full CSRs for the purposes of “bona fide scientific research” that contribute to the scientific understanding of the disease, target, or compound class. Pfizer will make available data from these trials 24 months after study completion. Patient level data will be anonymized in accordance with applicable privacy laws and regulations. CSRs will have personally identifiable information redacted.

Data requests are considered from qualified researchers with the appropriate competencies to perform the proposed analyses. Research teams must include a biostatistician. Data will not be provided to applicants with significant conflicts of interest, including individuals requesting access for commercial/competitive or legal purposes.

#### 10.1.7. Data Quality Assurance

All participant data relating to the study will be recorded on printed or electronic CRF unless transmitted to the sponsor or designee electronically (eg, laboratory data). The investigator is responsible for verifying that data entries are accurate and correct by physically or electronically signing the CRF.

Guidance on completion of CRFs will be provided in the CRF Completion Requirements document.

The investigator must ensure that the CRFs are securely stored at the study site in encrypted electronic and/or paper form and are password protected or secured in a locked room to prevent access by unauthorized third parties.

The investigator must permit study-related monitoring, audits, IRB/EC review, and regulatory agency inspections and provide direct access to source data documents. This verification may also occur after study completion. It is important that the investigator(s) and their relevant personnel are available during the monitoring visits and possible audits or inspections and that sufficient time is devoted to the process.

Monitoring details describing strategy, including the definition of study-critical data items and processes (eg, risk-based initiatives in operations and quality, such as risk management and mitigation strategies and analytical risk-based monitoring), methods, responsibilities, and requirements, including handling of noncompliance issues and monitoring techniques (central, virtual, or on-site monitoring), are provided in the data management plan and monitoring plan maintained and utilized by the sponsor or designee.

The sponsor or designee is responsible for the data management of this study, including quality checking of the data.

Records and documents, including signed ICDs, pertaining to the conduct of this study must be retained by the investigator for 15 years after study completion unless local regulations or institutional policies require a longer retention period. No records may be destroyed during the retention period without the written approval of the sponsor. No records may be transferred to another location or party without written notification to the sponsor. The investigator must ensure that the records continue to be stored securely for as long as they are maintained.

When participant data is to be deleted, the investigator will ensure that all copies of such data are promptly and irrevocably deleted from all systems.

The investigator will notify the sponsor or its agents immediately of any regulatory inspection notification in relation to the study. Furthermore, the investigator will cooperate with the sponsor or its agents to prepare the investigator site for the inspection and will allow the sponsor or its agent, whenever feasible, to be present during the inspection. The investigator site and investigator will promptly resolve any discrepancies that are identified between the study data and the participant's medical records. The investigator will promptly

provide copies of the inspection findings to the sponsor or its agent. Before response submission to the regulatory authorities, the investigator will provide the sponsor or its agents with an opportunity to review and comment on responses to any such findings.

#### **10.1.8. Source Documents**

Source documents provide evidence for the existence of the participant and substantiate the integrity of the data collected. Source documents are filed at the investigator site.

Data reported on the CRF or entered in the electronic CRF (eCRF) that are transcribed from source documents must be consistent with the source documents or the discrepancies must be explained. The investigator may need to request previous medical records or transfer records, depending on the study. Also, current medical records must be available.

Definition of what constitutes source data, and its origin can be found in the Source Document Locator, which is maintained by the sponsor.

Description of the use of the computerized system is documented in the Data Management Plan, which is maintained by the sponsor.

The investigator must maintain accurate documentation (source data) that supports the information entered into the CRF.

The sponsor or designee will perform monitoring to confirm that data entered into the CRF by authorized site personnel are accurate, complete, and verifiable from source documents; that the safety and rights of participants are being protected; and that the study is being conducted in accordance with the currently approved protocol and any other study agreements, the ICH GCP guidelines, and all applicable regulatory requirements.

#### **10.1.9. Study and Site Closure**

The study start date is the date on which the clinical study will be open for recruitment of participants.

The first act of recruitment is the date of the first participant's first visit and will be the study start date.

The sponsor designee reserves the right to close the study site or terminate the study at any time for any reason at the sole discretion of the sponsor, including (but not limited to) regulatory authority decision, change in opinion of the IRB/EC, or change in benefit-risk assessment. Study sites will be closed upon study completion. A study site is considered closed when all required documents and study supplies have been collected and a study site closure visit has been performed.

The investigator may initiate study site closure at any time upon notification to the sponsor if requested to do so by the responsible IRB/EC or if such termination is required to protect the health of study participants.

Reasons for the early closure of a study site by the sponsor may include but are not limited to:

- Failure of the investigator to comply with the protocol, the requirements of the IRB/EC or local health authorities, the sponsor's procedures, or GCP guidelines;
- Inadequate recruitment of participants by the investigator;
- Discontinuation of further study intervention development.

If the study is prematurely terminated or suspended, the sponsor shall promptly inform the investigators, the ECs/IRBs, the regulatory authorities, and any CRO(s) used in the study of the reason for termination or suspension, as specified by the applicable regulatory requirements. The investigator shall promptly inform the participant and should assure appropriate participant therapy and/or follow-up.

Study termination is also provided for in the clinical study agreement. If there is any conflict between the contract and this protocol, the contract will control as to termination rights.

#### **10.1.10. Publication Policy**

The results of this study may be published or presented at scientific meetings by the investigator after publication of the overall study results or 1 year after end of the study (or study termination), whichever comes first.

The investigator agrees to refer to the primary publication in any subsequent publications such as secondary manuscripts, and submits all manuscripts or abstracts to the sponsor 30 days before submission. This allows the sponsor to protect proprietary information and to provide comments and the investigator will, on request, remove any previously undisclosed confidential information before disclosure, except for any study or Pfizer intervention related information necessary for the appropriate scientific presentation or understanding of the study results.

For all publications relating to the study, the investigator will comply with recognized ethical standards concerning publications and authorship, including those established by the International Committee of Medical Journal Editors.

The sponsor will comply with the requirements for publication of the overall study results covering all investigator sites. In accordance with standard editorial and ethical practice, the sponsor will support publication of multicenter studies only in their entirety and not as individual site data. In this case, a coordinating investigator will be designated by mutual agreement.

Authorship of publications for the overall study results will be determined by mutual agreement and in line with International Committee of Medical Journal Editors authorship requirements.

If publication is addressed in the clinical study agreement, the publication policy set out in this section will not apply.

#### **10.1.11. Sponsor's Medically Qualified Individual**

The contact information for the sponsor's MQI for the study is documented in the study contact list located in the study team on demand (SToD) system.

To facilitate access to the investigator and the sponsor's MQI for study-related medical questions or problems from nonstudy healthcare professionals, participants are provided with an ECC at the time of informed consent. The ECC contains, at a minimum, (a) protocol and study intervention identifiers, (b) participant's study identification number, (c) site emergency phone number active 24 hours/day, 7 days per week, and (d) Pfizer Call Center number.

The ECC is intended to augment, not replace, the established communication pathways between the participant, and their investigator and site staff, and between the investigator and sponsor study team. The ECC is only to be used by healthcare professionals not involved in the research study, as a means of reaching the investigator or site staff related to the care of a participant. The Pfizer Call Center number is to be used when the investigator and site staff are unavailable. The Pfizer Call Center number is not for use by the participant directly, if a participant calls that number directly, they will be directed back to the investigator site..

## 10.2. Appendix 2: Clinical Laboratory Tests

The following safety laboratory tests will be performed at times defined in the [SoA](#) section of this protocol. Additional laboratory results may be reported on these samples as a result of the method of analysis or the type of analyzer used by the clinical laboratory, or as derived from calculated values. These additional tests would not require additional collection of blood. Unscheduled clinical laboratory measurements may be obtained at any time during the study to assess any perceived safety concerns.

**Table 10. Protocol-Required Safety Laboratory Assessments**

Hematology Panel	Chemistry Panel	Coagulation Panel 	Urinalysis 	Hepatitis Screening	Pregnancy Tests
WBC count with differential including blast count 	Sodium	INR or prothrombin time (PT)	pH	Hepatitis B surface antigen (HbsAg)	For female participants of childbearing potential, beta-human chorionic gonadotropin (β-HCG) serum or urine pregnancy test
	Potassium	Activated partial thromboplastin time or partial thromboplastin time (APTT or PTT)	Protein or albumin	Antibody to hepatitis C virus (anti-HCV)	
Hemoglobin	Magnesium		Urine protein to creatinine ratio 		
Platelet count	Calcium		Blood/hemoglobin		
	Creatinine		Ketones or acetone		
	Albumin				
	Alanine aminotransferase (ALT)				
	Aspartate aminotransferase (AST)				
	Glucose				
	Phosphorus				
	Total Bilirubin				
	Direct bilirubin only if total is elevated				

**Table 10. Protocol-Required Safety Laboratory Assessments**

Hematology Panel	Chemistry Panel	Coagulation Panel 	Urinalysis 	Hepatitis Screening	Pregnancy Tests
	Blood urea nitrogen (BUN) or urea				
	Uric acid or urate				
	Alkaline phosphatase				
	Lactate dehydrogenase (LDH)				
	Gamma-glutamyl transpeptidase (GGT)				
	Total protein				
	Amylase and/or Lipase 				

1. Preferably absolute values will be recorded in the CRF. Percentage will be recorded only if the absolute value is not reported at the local laboratory.
2. Coagulation: includes PT/INR (collected at screening, up to 72 hours predose of day 1 of each cycle and EOT). PTT or APTT required at screening and end-of-treatment visits only.
3. Urinalysis: conducted at screening, within 72 hours prior to dosing of Cycle 4 Day 1, and the end-of-treatment visit. Urine protein to creatinine ratio will be calculated at screening and End of treatment only.
4. Both amylase and lipase are required. However, at sites where one or the other is not performed, either the amylase or lipase test will be done. The same test will be performed throughout the study.
5. In the event the site laboratory does not perform urine protein measurements, a urine albumin to creatinine ratio will be obtained and recorded in the CRF.

The investigator must review the laboratory report, document this review, and record any clinically relevant changes occurring during the study in the AE section of the CRF.

## 10.3. Appendix 3: Adverse Events: Definitions and Procedures for Recording, Evaluating, Follow-up, and Reporting

### 10.3.1. Definition of AE

#### AE Definition

- An AE is any untoward medical occurrence in a patient or clinical study participant, temporally associated with the use of study intervention, whether or not considered related to the study intervention.
- NOTE: An AE can therefore be any unfavorable and unintended sign (including an abnormal laboratory finding), symptom, or disease (new or exacerbated) temporally associated with the use of study intervention.

#### Events Meeting the AE Definition

- Any abnormal laboratory test results (hematology, clinical chemistry, or urinalysis) or other safety assessments (eg, ECG, radiological scans, vital sign measurements), including those that worsen from baseline, considered clinically significant in the medical and scientific judgment of the investigator. Any abnormal laboratory test results that meet any of the conditions below must be recorded as an AE:
  - Is associated with accompanying symptoms;
  - Requires additional diagnostic testing or medical/surgical intervention;
  - Leads to a change in study dosing (outside of any protocol-specified dose adjustments) or discontinuation from the study, significant additional concomitant drug treatment, or other therapy.
- Exacerbation of a chronic or intermittent preexisting condition, including an increase in either frequency and/or intensity of the condition.
- New conditions detected or diagnosed after study intervention administration, even though it may have been present before the start of the study.
- Signs, symptoms, or the clinical sequelae of a suspected drug-drug interaction.
- Signs, symptoms, or the clinical sequelae of a suspected overdose of either study intervention or a concomitant medication. Overdose per se will not be reported as an AE/SAE unless it is an intentional overdose taken with possible suicidal/self-harming intent. Such overdoses should be reported regardless of sequelae.

#### Events NOT Meeting the AE Definition

- Any clinically significant abnormal laboratory findings or other abnormal safety assessments which are associated with the underlying disease, unless judged by the investigator to be more severe than expected for the participant's condition.
- The disease/disorder being studied or expected progression, signs, or symptoms of the disease/disorder being studied, unless more severe than expected for the participant's condition.
- Worsening of signs and symptoms of the malignancy under study should be recorded as AEs in the appropriate section of the CRF. Disease progression assessed by measurement of malignant lesions on radiographs or other methods should not be reported as AEs.
- Medical or surgical procedure (eg, endoscopy, appendectomy): the condition that leads to the procedure is AE.
- Situations in which an untoward medical occurrence did not occur (social and/or convenience admission to a hospital).
- Anticipated day-to-day fluctuations of preexisting disease(s) or condition(s) present or detected at the start of the study that do not worsen.

#### 10.3.2. Definition of SAE

If an event is not an AE per definition above, then it cannot be an SAE even if serious conditions are met (eg, hospitalization for signs/symptoms of the disease under study, death due to progression of disease).

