##### **8.4.1. Time Period and Frequency for Collecting AE and SAE Information**

The time period for actively eliciting and collecting AEs and SAEs (“active collection period”) for each participant begins from the time the participant provides informed consent, which is obtained before undergoing any study related procedure and/or receiving study intervention, through and including a minimum of 9 weeks after the last administration of the study intervention, except as indicated below, after the last administration of the study intervention.

For participants who are screen failures, the active collection period ends when screen failure status is determined.

The “active collection period” for VOD/SOS is the entire duration of study participation, including the long term follow-up period, regardless of whether new anti-cancer treatment is initiated. All cases of VOD/SOS will be reported in the CRF for up to 2 years from Cycle 1 Day 1 and must be reported as SAEs (recorded on the CRF and CT SAE Report Form).

Follow-up by -the investigator continues throughout the active collection period and until the AE or SAE or its sequelae resolve or stabilize at a level acceptable to the investigator.

When a clinically important AE remains ongoing at the end of the active collection period, follow-up by the investigator continues until the AE or SAE or its sequelae resolve or stabilize at a level acceptable to the investigator and Pfizer concurs with that assessment.

If the participant withdraws from the study and also withdraws consent for the collection of future information, the active collection period ends when consent is withdrawn.

If a participant permanently discontinues or temporarily discontinues study intervention because of an AE or SAE, the AE or SAE must be recorded on the CRF and the SAE reported using the CT SAE Report Form.

Investigators are not obligated to actively seek information on AEs or SAEs after the participant has concluded study participation. However, if the investigator learns of any SAE, including a death, at any time after a participant has completed the study, and they consider the event to be reasonably related to the study intervention, the investigator must promptly report the SAE to Pfizer using the CT SAE Report Form.

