#### **8.4.7. Disease Related Events and/or Disease Related Outcomes Not Qualifying as SAEs**

The following disease related events (DREs) are common in participants with ALL independent of exposure to study intervention, can be serious/life threatening:

- Febrile neutropenia;
- Neutropenic sepsis;
- Disease progression.
- The following occurring post HSCT and after discontinuation of inotuzumab ozogamicin:
  - Acute GvHD;
  - Infection requiring IV antibiotics;
  - Hemorrhage/bleeding;
  - Weight loss/anorexia;
  - Acute kidney injury;

- Nausea/vomiting/diarrhea;
- Thrombocytopenia/anemia.

Because these events are typically associated with the disease under study, they will not be reported according to the standard process for expedited reporting of SAEs even though the event may meet the definition of an SAE, unless the Investigator believes that there is a causal relationship between the investigational product. These events will be recorded on the corresponding CRF page in the participant's CRF within the appropriate time frame.

NOTE: However, if either of the following conditions applies, then the event must be recorded and reported as an SAE (instead of a DRE):

- The event is, in the investigator's opinion, of greater intensity, frequency, or duration than expected for the individual participant.

OR

- The investigator considers that there is a reasonable possibility that the event was related to study intervention.
- Grade 5 (or with an outcome of fatal).

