**g. Other situations:**

- Medical or scientific judgment should be exercised by the investigator in deciding whether SAE reporting is appropriate in other situations, such as significant medical events that may jeopardize the participant or may require medical or surgical intervention to prevent one of the other outcomes listed in the above definition. These events should usually be considered serious.
- Examples of such events include invasive or malignant cancers, intensive treatment in an emergency room or at home for allergic bronchospasm, blood dyscrasias or convulsions that do not result in hospitalization, or development of drug dependency or drug abuse.
- Progression of the malignancy under study (including signs and symptoms of progression) should not be reported as an SAE unless the outcome is fatal within the active collection period. Hospitalization due to signs and symptoms of disease progression should not be reported as an SAE. If the malignancy has a fatal outcome during the study, the event leading to death must be recorded as an

AE on the CRF, and as an SAE with CTCAE Grade 5 (see the [Assessment of Intensity](#) section) if it occurs during the active collection period.

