3.5. Safety Endpoints

Safety endpoints will be summarized based on the on-treatment period unless otherwise specified.

On-treatment is defined as the time from the first dose of study treatment through minimum (9 weeks after the last administration of the investigational product, start day of new anti-cancer therapy – 1 day). The start date of new anti-cancer therapy after the first dose of study treatment is derived as outlined in [Section 5.2.5](#). Adverse events occurring on the same day as the first dose of study treatment will be considered to have occurred during the on-treatment period. All other assessments which occur on the same day as the first dose of study treatment will be considered baseline assessments (see [Section 3.4](#) for the definition of baseline). If the exact time is collected, the last assessment before the time of first dose of study treatment will be considered as baseline assessments.

Safety data collected outside the on-treatment period as described above will be listed but not summarized.

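### Protocol 10.3.2 both rules out and requires SAE reporting of fatal disease progression, which leaves the all-causality Grade 5 and serious TEAE rows open to inconsistent coding

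*Protocol*

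**What the plan says.** Four protocol texts bear on a death from leukaemia progression in the active collection period. That period runs from consent "through and including a minimum of 9 weeks after the last administration of the study intervention" (Protocol 8.4.1).

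- **Protocol 10.3.1, events not meeting the AE definition.** The exclusion covers "The disease/disorder being studied or expected progression, signs, or symptoms of the disease/disorder being studied, unless more severe than expected" for the participant's condition. It makes no exception for a fatal outcome.
- **Protocol 10.3.2, first paragraph.** An event that is not an AE "cannot be an SAE even if serious conditions are met (eg, hospitalization for signs/symptoms of the disease under study, death due to progression" of disease. Progression death is thus a named example of something that is not an SAE.
- **Protocol 10.3.2, item g.** Progression "should not be reported as an SAE unless the outcome is fatal within the active collection period". If the malignancy is fatal, the event leading to death goes down as an "AE on the CRF, and as an SAE with CTCAE Grade 5", the SAE part applying when it falls in the active collection period.
- **Protocol 8.4.7.** Disease progression is on the list of disease related events that skip expedited reporting. If a listed condition applies, "then the event must be recorded and reported as an SAE (instead of a DRE"), and one of those conditions is "Grade 5 (or with an outcome of fatal").

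On the analysis side, SAP 6.6.1 counts participants with a serious TEAE and with a Grade 5 TEAE. It uses the seriousness and grade on the investigator's AE page and has no rule for fatal progression.

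**The concern.** The same death gets opposite instructions within one section of the protocol. Two things depend on which instruction a site follows.

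1. **Reporting.** Protocol 8.4.1.1 requires SAEs to reach the sponsor within 24 hours. A site acting on the first paragraph of 10.3.2 would not send a report that item g and 8.4.7 require.
2. **Tabulation.** The SAP does not re-derive seriousness or grade. A progression death coded as Grade 5 at one site and left off the AE page at another would make the all-causality Grade 5 and serious TEAE rows a mixture of two conventions. Confirming safety is one of the stated purposes of this post-approval study, so these rows matter.

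**Working it through.** The plan states no figure on this point, so there is nothing to reproduce. The check sets the texts side by side and then works out the shift per participant.

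**Step 1: apply each text to one case, a participant who dies of expected leukaemia progression six weeks after the last dose, with no new therapy.**

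| Text | AE? | SAE? | Grade 5? |
|---|---|---|---|
| 10.3.1 exclusion | No, unless worse than expected | – | – |
| 10.3.2, first paragraph | No (named example) | No | – |
| 10.3.2, item g | Yes | Yes | Yes |
| 8.4.7 | – | Yes | Fatal outcome is the trigger |

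The first two rows and the last two cannot both be followed. The first paragraph of 10.3.2 is conditional on the event not being an AE, but that does not resolve the conflict: it names progression death as meeting the condition, and the 10.3.1 exclusion has no fatal exception. Its other example, hospitalization for signs and symptoms of the disease, agrees with item g. Only the death example conflicts.

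**Step 2: which events reach the TEAE tables.** SAP 3.5 sets the window: "On-treatment is defined as the time from the first dose of study treatment through minimum (9 weeks after the last administration", or the day before new anti-cancer therapy if that is earlier. SAP 3.5.1 decides by event start date. Fatal progression that starts after new therapy is therefore listed but not counted in these rows.

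**Step 3: shift per participant.** The denominator is 44 (Protocol 9.2; SAP 5.1.1). For k participants whose only Grade 5 event is fatal progression, the Grade 5 row moves by 100 × k/44:

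| k (assumed) | Shift in Grade 5 TEAE row |
|---|---|
| 1 | 2.3 points |
| 2 | 4.5 points |
| 4 | 9.1 points |
| 6 | 13.6 points |

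The serious TEAE row moves only for participants with no other serious TEAE, so its shift is equal or smaller. The values of k are illustrative.

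**Step 4: outputs that do not depend on this coding.** CR/CRi, OS and PFS do not use AE seriousness or grade. The deaths summary in SAP 6.6.2 draws on the Notice of Death and Survival Follow-Up CRFs.

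**The case against.** The best defence is that a specific rule outranks a general one. The first paragraph of 10.3.2 is a general conditional sentence with an example, while item g deals with exactly this case in mandatory terms and 8.4.7 independently agrees. Section 10.3.1 is not a flat exclusion either: it exempts progression worse than expected and asks for worsening signs and symptoms of the malignancy to be recorded as AEs. This shows the probable intent, and nothing in the documents shows that sites do in fact differ. But the protocol states no precedence, and a site reading 10.3.2 from the top meets the prohibition first.

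The second defence is that other outputs limit the damage, and this largely stands. SAP 6.6.1 gives the high-level summary for treatment-related as well as all-causality TEAEs, with preferred-term tables by grade, so an event coded as progression can be seen. SAP 6.6.2 tabulates the primary reason for death and lists date and cause of death with dosing information. The match is only partial, because that table splits deaths at 28 days after last dose while the TEAE window runs up to 9 weeks.

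A reader might infer three stronger things that the documents do not support.

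- **That fatal toxicity cannot be interpreted.** The treatment-related rows should be little affected, and the deaths table is independent of AE coding.
- **That comparison with Study B1931022 is spoiled.** Neither document plans to compare Grade 5 rates with that study, gives its overall Grade 5 rate, or says how it coded fatal progression.
- **That some 3 to 10 of 44 participants would move.** That range comes from a window of 8.9 + 9 = 17.9 weeks (4.12 months) and an exponential OS curve with the 7.7-month median: 1 − exp(−ln 2 × 4.12/7.7) = 0.31, or 13.6 of 44. A 12-week window (2.76 months) gives 0.22, or 9.7 of 44. Multiplying by an assumed progression share of 30% to 70% gives 2.9 to 9.5. The share has no source in the documents, one median-based window is applied to everyone, the hazard is assumed constant, and all sites are assumed to switch together.

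**Conclusion.** The contradiction is real and confined to safety reporting and two all-causality table rows. Its size can be stated only per participant: 2.3 percentage points in the Grade 5 TEAE row for each participant whose only Grade 5 event is fatal progression, and the same or less in the serious TEAE row. This assumes 44 treated participants and an event that starts within the SAP on-treatment window. No total can be given, because the documents contain no expected number of such deaths.

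This is an inconsistency of wording with a modest effect on tabulation. It is worth correcting because it changes what sites must send within 24 hours and because the correction is cheap. It gives no reason to doubt the primary or survival analyses.

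**What to change.** 1. **Protocol 10.3.2, first paragraph.** Remove the progression-death example, or add that it applies except as stated in item g and Section 8.4.7.
2. **Protocol 10.3.1.** Add the same cross-reference for fatal outcome to the exclusion of expected progression. Without it, the general rule in 10.3.2 would still reach the same death by way of the AE definition.
3. **SAP 6.6.1.** Show the all-causality Grade 5 and serious TEAE rows twice: as coded, and without fatal progression of the leukaemia under study.
4. **Before database lock.** Check the reasons for death on the Notice of Death CRF against the AE pages, and query mismatches.

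The cost is a clarification letter, two extra table rows and some queries. The letter does not recode deaths already entered, so step 4 is needed even if the wording is corrected promptly.
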